## PROTOCOL SYNOPSIS

Protocol Title:	
Site Numbers & Names:	001: UCLA Rheumatology 002: UCSD Rheumatology
Research Hypothesis:	Primary: Abatacept will improve lupus inflammatory polyarthritis in patients by 16 weeks of treatment.
Study Rationale	
Inflammatory polyarthritis is common in people with SLE, with swollen, tender joints occurring in up to 88% of patients . Inflammatory arthritis often improves on aggressive therapies, including glucocorticoids, mycophenolate, and cyclophosphamide , sometimes with azathioprine, and occasionally with methotrexate or leflunomide. The use of abatacept by the subcutaneous route is a highly attractive alternative for treatment of lupus arthritis for the following reasons.
 
1) Abatacept is effective in rheumatoid arthritis, which lupus arthritis resembles ,
 
2) The synovitis of SLE depends on activated innate and adaptive immunity, with antigen-presenting cells (APC) activating effector T cells, which activate B cells. Together, these cells secrete pro-inflammatory cytokines including IFN type 1, IFNgamma and IL-17 . Interruption of CD80/86-CD28 interactions by abatacept should block APC/T cell signals that drive inflammation, without blocking regulatory cell generation that is anti-inflammatory.
 
3) A prospective controlled trial of abatacept in SLE showed a lower flare rate in patients with polyarthritis who received abatacept compared to patients with polyarthritis who received placebo .
 
4) A recently published retrospective study of 6 patients with rhupus (satisfying ACR criteria for both rheumatoid arthritis and systemic lupus erythematosus) showed that all responded to abatacept with decrease in Clinical Disease Activity Index (a validated measure of disease activity in rheumatoid arthritis) and minimal adverse events.

Study Objectives:	
Primary: Improvement of lupus inflammatory polyarthrits measured by <math>\geq 20\%</math> improvement in tender and swollen 28 joint counts at 16 weeks.
 
Secondary:
 
 
1. Mean and median joint counts in treated vs placebo patients at 16 weeks, compared to baseline scores.
 
2. Proportion of patients who achieve improvement in SLEDAI 2K at 16 weeks of <math>>3</math> points.
 
3. Mean and median changes in CDAI comparing abatacept to controls at 16 weeks.
 
4. Changes in a) synovitis, b) tenosynovitis and c) erosions measured by high-energy ultrasound with Doppler flow at zero and 16 weeks.
 
5. Proportion of patients with BILAG A in any system other than musculoskeletal at week 16.
 
6. Proportion of patients with no significant increase in physician global assessment (defined as <math><0.8</math> on a 1-10 scale) at 16 weeks.
 
7. Steroid sparing effect of abatacept, measured as ability to taper prednisone to <math>\leq 10</math>mg/day by week 16.
 
8. Effects on fatigue at 16 weeks as measured by the FACIT fatigue score instrument
 
9. Effects on quality of life at 16 weeks as measured by the SF 36
 
10. Safety, measured in standard methods as AE and SAE, including likelihood that the AE/SAE was related to the study biologic.
 
11. Time to response, measured as time to <math>\geq 20\%</math> decrease in joint counts (sum of tender and swollen joints) at zero, 4, 8, 12, and 16 weeks.
 
12. Change in peripheral blood T cell compartments indicating decline in pro-inflammatory profiles, i.e., we expect decrease in CD4+ effector T cells that make IFNgamma (TH1) and IL-17 (TH17) and increase in ratio of Treg to Teff, as well as decreased function of Thelper and increased functions of Tregs. CD4+CD25+ Foxp3+ and CD8+Foxp3+ will be the definition of regulatory T cells. These will be measured at zero and 16 weeks.
 
13. Change in anti-DNA and total IgG levels, as well as rise in serum complement levels as disease improves and fewer B cells are activated: measure these at zero, 8 and 16 weeks.
 
14. Effects of abatacept on serum levels of BLyS (BAFF) at baseline, 8 and 16 weeks. As numbers of activated B cells and plasmablasts fall, we expect an increase in BLyS levels
 

--------------------------	---

Study Design:	Randomized trial of 32 SLE patients treated with subcutaneous abatacept 125mg sq once a week vs. 32 placebo treated subjects over a 16 week period. Patients will be seen every 4 weeks from baseline. One half of patients will be recruited at UCLA and one-half at UCSD. We expect 30 patients in each group to complete the 16 week study.
Study Schema Drugs / Doses / Length of Treatment)	Abatacept 125 mg or placebo will be administered subcutaneously once a week for 16 weeks. There will be a telephone follow up 2 months after the last injection to capture post-treatment adverse events.
Accrual Goal: (Total number of subjects)	64 (32 at UCLA and 32 at UCSD)
Accrual Rate: (Number of subjects expected per month)	2-3 subjects per month at each site
FPFV: April 1, 2015 LPFV: March 31, 2018  Follow Up: 16 weeks per patient plus 8 weeks of observation for adverse events	
Correlative Studies: These will be performed at the UCLA site only	
1) Biomarkers: a) T cell numbers and phenotypic and functional characteristic in PBMC measured at week 0 and 16. These will include for T cells CD4+, CD3+, CD25+, CD8+, Foxp3+ and cytoplasmic stains for IFNgamma, IL2, IL-17, IL21 and IL-10.
 
b) B cell numbers and subsets, including naïve, activated and plasmablasts.
 
c) Ability of autologous CD4+CD25hi T cells to suppress proliferation of CD4+CD25- T cells.
 
d) Cytokines in serum: IFNgamma, IL-6, IL-10, IL-17, IL23 and BLyS
 
2) Ultrasound with power Doppler of joints assessing synovitis, tenosynovitis (18 joints) and erosions at week 0 and 16.

Inclusion Criteria	
 
1. Meet at least 4 of the 11 American College of Rheumatology (ACR) 1997 criteria for classification of SLE (see Appendix 1). OR meet the recent classification recommended by SLICC (Appendix 2)
 
2. <math>\geq 3</math> swollen and tender joints on 2 examinations at least 2 weeks apart and no more than 8 weeks apart.
 
3. SLEDAI2K score <math>\geq 4</math> indicating active disease.
 
4. Documented positive ANA (<math>\geq 1:80</math>) and/or anti-dsDNA during course of SLE.
 
5. Men and women, at least 18 years of age. Women of childbearing potential must use adequate method(s) of contraception to avoid pregnancy throughout the study and for up to 2 months after last study drug dose. They must have a negative serum or urine pregnancy test prior to the start of study medication.
 
6. Background therapies allowed: antimalarials (dose constant for <math>\geq</math> one month before study entry and during 16 weeks of trial), methotrexate (same criteria as for antimalarials), azathioprine (same criteria), mycophenolate (same criteria), leflunomide (same criteria). During the screening period and for up to 6 weeks after randomization, a daily prednisone (or equivalent) regimen of up to 20 mg daily may be initiated to treat the moderate to severe disease activity present at screening. The initial steroid regimen is not required if investigators or patients believe that the risks would outweigh the potential benefits. Patients who do not take any glucocorticoids during the study will be included in the treatment groups and analysis.
 
 
*Steroids should be tapered to a target dose of no more than 10 mg/day of prednisone (or equivalent) by the end of Week 8 (Day 56). The steroid regimen should be tapered as quickly as safely possible. Prednisone dose requirements higher than 10 mg daily at the 8 week visit will cause the patient to be ruled a non-responder for the abatacept treatment arm.

---------------------------	--

Exclusion Criteria:	
 
1. Subjects with active infection requiring oral or IV antibiotics within one month of first dose of study medication.
 
2. Subjects with BILAG A in any system outside the musculoskeletal system.
 
3. Subjects with positive quantiferon Gold test in the absence of treatment for tuberculosis.
 
4. Subjects with positive tests for active infection with hepatitis B or C during the past 6 months. Any confirmed positive test for HIV at any time prior to entry into this study.
 
5. Subjects with active glomerulonephritis (<math>>3</math> g protein/24h and/or active urine sediment).
 
6. Subjects with active CNS disease.
 
7. Subjects with any other serious disease that would require immunosuppressive or parenteral anti-microbial therapy outside the study protocol.
 
8. Inability to self-administer subcutaneous injections, to comply with instructions, or to keep appointments for study visits.
 
9. Treatment with rituximab within the past 6 months (B cells must be detectable in peripheral blood at onset of treatment with study biologic), belimumab within the past 3 months, cyclophosphamide within the past 3 months.
 
10. Treatment with any other immunomodulatory biologic or cyclophosphamide during treatment with abatacept is not allowed.
 
11. Patients requiring <math>>20</math> mg of prednisone daily.
 
12. Women who are pregnant or breast feeding.
 
13. Women of child bearing potential unwilling or unable to use an acceptable method to avoid pregnancy for the entire study period and for up to 2 months after last study drug.
 
14. Subjects with a history of cancer within the last five years (other than non-melanoma skin cell cancers cured by local resection).
 
15. Any laboratory test results that, in the opinion of the Investigator, might place the subject at unacceptable risk for participation in this study.
 

Criteria for Evaluation: (Efficacy, safety, stopping rules, etc.)	See text
Statistics:	See text

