## **2 STUDY OBJECTIVES**

### **2.1 Primary Objective**

Improvement of lupus inflammatory polyarthritis measured by proportion of patients who achieve >=20% improvement in tender and swollen 28 joint counts at 16 weeks.

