SLE patients with 3 or more swollen and tender joints and moderate or severe lupus activity (SLEDAI 2K score 4 or greater) will be eligible for this study. In addition, patients must have current or historical documented positive Antinuclear Antibody (ANA) and/or anti-double stranded deoxyribonucleotide antibody (anti-dsDNA).

The established SLE therapy (as allowed by the study) at study entry will be continued as background therapy. Background therapy should be kept stable throughout the study, although increase in prednisone to not more than 30 mg a day, which much be tapered to  $\leq 10$  mg daily by 8 weeks, will be permitted. Tapering of prednisone dose at any time will be permitted. Dosage increases in antimalarial, or any other non-glucocorticoid immunosuppressives, or introduction of any of these or a biologic agent as a new therapy (not allowed by the protocol) will be regarded as a treatment failure. Subjects requiring prednisone or equivalent doses  $>10$  mg a day at/after the 8 week visit will be regarded as treatment failures.

The US will be performed by a rheumatologist with expertise in musculoskeletal ultrasound and images will be digitally saved. US will be performed at UCLA only, for the 32 patients enrolled there. Each UCLA patient will have ultrasounds performed on the same machine by the same ultrasonographer at baseline and 16 weeks.

18-Joint US Scoring System (bilat wrists, bilat MCPs 2-5, bilat PIPs 2-5)

JOINT	VIEW	Power Doppler Synovitis	B-mode Synovial Hypertrophy	Tendons	Erosions
Wrists	Dorsal Longitudinal Midline (Radio carpal, intercarpal)	X	X		
MCPs (2-5)	Dorsal Orthogonal	X	X		X (MCP 1,2, and 5)
	Volar Longitudinal	X	X	X	
	Dorsal Paratendon	X	X	X	
PIP/IP (2-5)	Volar Longitudinal	X	X	X	

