#### **6.4.1 Primary Efficacy Assessment**

1. Proportion of patients who achieve  $\geq 20\%$  Improvement in tender and swollen joint counts at 16 weeks

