## **8 STATISTICAL CONSIDERATIONS**

### **8.1 Sample Size Determination**

We based our sample sizes on the preliminary data (unpublished): SLE patients with arthritis at the start of a treatment had a mean score on 66-joint count of  $21 \pm 8.2$ . There was a decrease to a mean of  $2.0 \pm 1.5$  after 12 weeks of various interventions in patients who reported they improved. For the study proposed here, if 67% of abatacept pts will achieve 20% improvement in swollen and tender joints vs. 30% of controls by week 16, n=28 per group (with p=0.05, power=0.8). Thus we plan 32 patients for abatacept over 16 weeks and 32 patients for placebo over 16 weeks, a total of 64. The dropout rate in the abatacept non-nephritis lupus trial was 35% (over 12 months). We anticipate one-third that in a 4 month trial, proposed, here – i.e. 12%. If we begin with 64 patients we should have 56 completers, thus approximately 28 in each group.

Thus, we will plan to recruit 32 SLE patients at UCLA and an additional 32 at UCSD (separate contract).

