### ***8.4.3 Efficacy Analyses***

The Fisher's exact test will be used to compare the percent of subjects achieving primary and secondary outcomes between two groups. Wilcoxon rank sum tests will be used to compare ordinal and quantitative outcomes between groups. Logistic regression will also be used to adjust for baseline clinical presentation and demographic factors. A site by treatment interaction effects will be included in the model to account for possible differences in treatment efficacy between our two sites. Bivariate analysis and nonparametric analysis (for example local polynomial regression or generalized additive model analysis) will be carried out to inspect the relationship between outcome and covariates. The goodness-of-fit of logistic models will be evaluated using the Hosmer-Lemeshow test. With the quantitative outcomes such as joint counts, ultrasound measurements, etc we will use Poisson regression to assess the treatment effect or linear regression for continuous outcomes. Poisson regression is a special case of generalized linear model and robust pseudo likelihood inference will be used in the analysis. We also will use multiple imputation technique to accommodate possible missing data at 12 and 24 weeks due to patients lost to follow up. The imputation model will include all baseline 12 week and 24 week outcomes and covariates to impute the missing outcomes . Analyses will be done with and without imputation.

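### Two steroid and rescue-drug failure rules of different scope are never tied to the joint-count primary endpoint, so a small group of patients can be scored either way

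*Combined protocol and SAP*

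**What the plan says.** Section 2.1 sets the primary objective: "Improvement of lupus inflammatory polyarthritis measured by proportion of patients who achieve" at least 20% improvement in the 28-joint counts at week 16. Section 6.4.1 repeats it ("Improvement in tender and swollen joint counts at 16 weeks"), and so does the Synopsis objective. Section 8.1 sizes the trial on the same quantity: "if 67% of abatacept pts will achieve 20% improvement in swollen and tender joints", against 30% of controls. Section 8.4.3 says that Fisher's exact test "will be used to compare the percent of subjects achieving primary and secondary outcomes between two groups". Section 8.3 lists the measures recorded but gives no responder algorithm. None of these places mentions treatment failure.

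Two other places define failure:

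- Synopsis, Inclusion Criterion 6 (steroid note): a prednisone requirement above 10 mg daily "at the 8 week visit will cause the patient to be ruled a non-responder for the abatacept treatment arm".
- Section 4.1: subjects requiring more than 10 mg "a day at/after the 8 week visit will be regarded as treatment failures". In addition, a dose increase in an antimalarial or other non-steroid immunosuppressive, or introduction of one of these or a biologic "as a new therapy (not allowed by the protocol) will be regarded as a treatment failure".

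On missing data, Section 8.4.3 says: "We also will use multiple imputation technique to accommodate possible missing data", and attributes the missing data to loss to follow-up.

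**The concern.** The two rules differ in timing (the week 8 visit only, or week 8 onward), in triggers (steroid only, or steroid plus background drugs), in label (non-responder, or treatment failure) and in the arm named. Neither says what it does to the Fisher comparison in Section 8.4.3.

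This matters because Section 1.2.2 says that corticosteroids, antimalarials, immunosuppressives and biologics treat lupus polyarthritis. The event that makes a patient a failure can also produce the joint improvement that makes the same patient a responder. Joint count alone credits that improvement to the assigned arm; a composite with failure does not. These are different treatment effects, and the choice between them should be fixed before anyone sees the codes.

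**Working it through.** **1. Scoring the same patient under each text.** Every patient below has at least 20% joint improvement at week 16.

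| Patient | Synopsis steroid note | Section 4.1 | Sections 2.1 and 6.4.1 |
|---|---|---|---|
| Needs >10 mg at the week 8 visit, abatacept | non-responder | failure | responder |
| Same, placebo | not named | failure | responder |
| ≤10 mg at week 8, needs >10 mg at week 12 | silent | failure | responder |
| Background immunosuppressive increased | silent | failure | responder |

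The two failure rules agree on the week 8 steroid trigger, apart from the arm wording. The last two rows are the gap: only Section 4.1 covers them, and nothing says that its label changes the primary score.

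**2. Can such patients occur?** Section 5.5.1 bars more than 10 mg after week 8, and Section 4.3.1 bars starting most of the relevant drugs. However, Section 4.2.3 allows rescue prednisone up to 20 mg to be considered for worsening disease at any time in the study, with no week limit. The group need not be empty.

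**3. The plan's own sample size.** Inputs from Section 8.1: 67% vs 30%, alpha 0.05, power 0.80. Sidedness is not stated; two-sided is assumed. With pooled variance and no continuity correction, the mean rate is (0.67 + 0.30)/2 = 0.485 and

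n = [1.960·√(2·0.485·0.515) + 0.842·√(0.67·0.33 + 0.30·0.70)]² / 0.37² = 27.4, rounded up to 28 per group.

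This matches the plan. The sample-size figure is not in error.

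**4. Sensitivity of power.** The documents give no failure rate. Let qa and qp be the assumed shares of joint-count responders who are rescored as failures on abatacept and placebo. The response rates become 0.67(1 − qa) and 0.30(1 − qp). Power is for the two-sided Fisher test at 0.05 by full enumeration, with 32 per arm, because Section 8.2 analyses all 64.

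| qa | qp | Rates | Power |
|---|---|---|---|
| 0 | 0 | 67.0% vs 30.0% | 82% |
| 2% | 2% | 65.7% vs 29.4% | 80% |
| 5% | 5% | 63.7% vs 28.5% | 77% |
| 10% | 10% | 60.3% vs 27.0% | 72% |
| 5% | 10% | 63.7% vs 27.0% | 81% |
| 10% | 20% | 60.3% vs 24.0% | 80% |
| 10% | 5% | 60.3% vs 28.5% | 68% |
| 10% | 30% | 60.3% vs 21.0% | 87% |
| 20% | 10% | 53.6% vs 27.0% | 51% |

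The Synopsis already reclassifies week 8 steroid need, so the share truly in dispute is smaller than the total failure share.

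**5. Sensitivity of a result.** The planned rates give 0.67 × 32 = 21.4 and 0.30 × 32 = 9.6 responders. Start from a hypothetical 21 vs 10 out of 32 each (Fisher p = 0.012):

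- One or two abatacept responders rescored: 20 vs 10, p = 0.023; 19 vs 10, p = 0.044.
- Both arms rescored: 20 vs 9, p = 0.011; 19 vs 9, p = 0.023; 18 vs 9, p = 0.042.
- Three on abatacept and none on placebo: 18 vs 10, p = 0.077.

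**The case against.** A reader might infer more than the documents support, in three ways.

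*That the two rules contradict each other.* They do not. The Synopsis is silent on later steroid need and on background drugs; it does not call those patients responders. It also refers to the text for its evaluation criteria and statistics, so it can be read as a short form of Section 4.1. For the same week 8 trigger one place says non-responder and the other treatment failure, which suggests that the terms mean the same thing. That is a reasonable guess, but no sentence says so. The mismatch between the rules is one of scope and label; the missing link to the endpoint remains.

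*That only abatacept patients are penalised.* Taken literally, the Synopsis says this. But Section 4.1 names no arm, and under Section 5.4 the trial stays blinded to its end except in emergencies, so sites could not apply a one-arm rule. It is probably loose drafting.

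*That the trial loses its power or its result.* The disputed patients must meet a trigger that is largely prohibited and still improve by 20% at week 16. If failures are twice as common on placebo, power stays at 80% to 81%. In the examples above, significance is lost only when three abatacept responders and no placebo responder are rescored; one placebo change alongside restores it (p = 0.042).

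The small group and the uncertain effect lower the priority. They do not supply the scoring rule.

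**Conclusion.** The point holds as a gap that should be fixed, not as a fatal contradiction. Joint count alone defines the primary endpoint, two failure rules of different scope sit beside it, and nothing connects them. Two statisticians could score a late steroid need or a background-drug change differently, and each could cite the protocol. Confidence in the missing link is high, since it is read directly from the text. The numerical effect is unknown: every failure share above is an assumption, and the direction depends on which arm has more failures. At assumed shares of 2% to 5% in both arms, power falls from 82% to between 80% and 77%.

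**What to change.** - Delete the reference to the abatacept arm from the Synopsis steroid note.
- State the Section 4.1 rule once, for both arms, and define a primary responder as a subject with at least 20% joint-count improvement at week 16 and no treatment failure. Use that definition in the Synopsis (objective and steroid note) and in Sections 2.1, 4.1, 6.4.1, 8.3 and 8.4.3.
- Assign failure status before unblinding.
- In Section 8.4.3, score treatment failures as non-responders even when the week 16 count is missing, as a stated exception to multiple imputation.
- Report joint-count-only response as a sensitivity analysis.
- Say in Section 8.1 which definition the 67% and 30% refer to.
- Align the rescue prednisone in Section 4.2.3 (up to 20 mg, no week limit) with the 10 mg limit after week 8 in Section 5.5.1.

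Keeping joint count alone as primary would also remove the ambiguity, provided that the Synopsis and Section 4.1 then say that failure does not affect the primary endpoint. The Synopsis wording favours the composite.

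The cost is wording plus one analysis change. Concomitant medication is already reviewed at every visit. A blinded judgement is needed on whether a steroid dose was required. Response rates fall somewhat, and power may fall by a few points, hold or rise, depending on failures by arm.

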## 1 INTRODUCTION

### 1.1 Research Hypothesis

Abatacept via subcutaneous injection will induce clinical response in inflammatory polyarthritis in patients with systemic lupus erythematosus.

### 1.2 Product Development Rationale

Abatacept is a recombinant fusion protein consisting of the extracellular domain of human CTLA4 and a fragment (hinge- CH2-CH3 domains) of the Fc domain of human IgG1 that has been modified to prevent complement fixation and antibody-dependent cellular cytotoxicity.

Abatacept is the first drug in a new class of agents termed “selective costimulation modulators.” Abatacept binds specifically to the CD80 and CD86 molecules, proteins prominently displayed on the surface of antigen-presenting cells (APCs). Activation of naive T cells during an immune response requires two stimuli from APCs. The first signal is antigen-specific; antigens are presented by APCs, with the signal transmitted to the T cell through the T cell’s antigen receptor. The second, or costimulatory, signal is not antigen-specific and is delivered following the engagement of a costimulatory ligand on the APC with a cognate receptor on the T cell.

A key costimulatory receptor on T cells is CD28. CD28 is constitutively expressed on resting T cells and binds to both CD80 (B7-1) and CD86 (B7-2) on the APC . A costimulatory signal is required not only for the full activation of naive T cells, but also may be required for the survival of memory and autoimmune effector cells . At 24 to 48 hours following T cell activation, the T cell expresses CTLA4 on its surface, which engages the CD80 and CD86 molecules on the APC surface interfering with CD28’s ability to bind to its ligands on the APC; CD80 and CD86 preferentially bind to CTLA4 with a much higher avidity than with CD28. Although the precise mechanisms are as yet unclear, CTLA4 expression is associated with a decrease in T cell activation.

After the T cell activity has been dampened, the CTLA4 recycles into the T cell’s cytoplasm. The CTLA4 section of abatacept binds specifically to CD80 and CD86 (B7-1 and B7-2, respectively) and down-modulates the CD28-mediated costimulation of T cells. Thus, abatacept uses a segment of a molecule that is part of the normal immune homeostatic mechanism to suppress T cell activity involved in the immunopathogenesis of autoimmune diseases. The FC region of abatacept was engineered with several point mutations designed to inactivate it. Because of these changes, abatacept does not mediate pathways such as antibody-dependent cell cytotoxicity or complement-dependent cytotoxicity .

